8. SOFTWARE

All analyses will be done using SAS Version 9.4 or higher.

10. APPENDIX

10.1. Summary of Statistical Analyses

Primary Efficacy Analysis:

Endpoint	Analysis Population	Statistical Method	Supportive Analysis	Subgroup Analysis	Other Analyses
Percent lowering of TG levels from baseline following 12 weeks of repeated IV doses of evinacumab in the subset of patients with a documented history of sHTG (TG ≥ 1000 mg/dL [11.3 mmol/L]), a TG level of at least 500 mg/dL (5.6 mmol/L) at screening, a history of acute pancreatitis, and without LOF mutations in genes in the LPL pathway.	FAS	MMRM	No	Yes	No

10.2. List of AESIs with Data Sources and Definitions of SMQ/CMQ

AESI	Using an e-CRF specific tick box on AE page	Using Standard MedDRA Query (SMQ)/company MedDRA Query (CMQ) or lab data
Anaphylactic reactions	Yes	No
General allergic events	No	SMQ “hypersensitivity” (broad and narrow) excluding the following preferred terms linked to local injection site reactions (“infusion site dermatitis”, “infusion site hypersensitivity”, “infusion site rash”, “infusion site urticaria”, “injection site dermatitis”, “injection site hypersensitivity”, “injection site rash”, “injection site urticaria”, “injection site vasculitis”) plus “idiopathic angioedema”
Infusion reactions	Yes	No
Pregnancy	Yes	No
Symptomatic overdose with investigational medicinal product	Yes	No
Neurocognitive events	No	CMQ for neurocognitive events as defined based on Regulatory Agency request for another lipid lowering program (See Table 4 in Appendix 10.2 for the list of terms)

New onset of diabetes (NOD)	No	
 At least 2 values of HbA1c $\geq 6.5\%$ during the TEAE period. NOTE: For patients with only a single measurement available during the TEAE period, a single value $\geq 6.5\%$ will be considered and qualify the patient as NOD by default. For patients with several HbA1c measurements but only with the last one $\geq 6.5\%$, this single value $\geq 6.5\%$ will be considered and qualify the patient as NOD by default. 
OR
 
 At least 2 values of fasting glucose ≥ 126 mg/dL (7.0 mmol/L). NOTE: For patients with only a single measurement available during the TEAE period, a single value ≥ 126 mg/dL (7.0 mmol/L) will NOT be considered and will NOT qualify the patient as NOD. For patients with several fasting glucose measurements but only with the last one ≥ 126 mg/dL (7.0 mmol/L), this single value ≥ 126 mg/dL (7.0 mmol/L) will NOT be considered and will NOT qualify the patient as NOD.
Pancreatitis	Yes	No

Table 4 CMQ “Neurocognitive disorders – FDA’s recommendation”

MedDRA level	MedDRA Term Label
PTCD	Amnesia
PTCD	Amnestic disorder
PTCD	Anterograde Amnesia
PTCD	Behavioural and Psychiatric Symptoms of Dementia
PTCD	Change in sustained attention
LLTCD	Cognitive Deterioration
PTCD	Cognitive Disorder
LLTCD	Confusion
LLTCD	Confusion Aggravated

MedDRA level	MedDRA Term Label
PTCD	Confusional State
PTCD	Delirium
PTCD	Dementia
PTCD	Dementia Alzheimer's type
LLTCD	Dementia Nos
LLTCD	Dementia Nos Aggravated
LLTCD	Dementia of the Alzheimer's type NOS
PTCD	Dementia with Lewy Bodies
PTCD	Disorientation
PTCD	Disturbance in attention
PTCD	Executive dysfunction
PTCD	Frontotemporal Dementia
LLTCD	Global Amnesia
PTCD	Illogical Thinking
PTCD	Impaired reasoning
PTCD	Incoherent
PTCD	Judgement impaired
PTCD	Memory Impairment
PTCD	Mental Impairment
LLTCD	Mental Impairment Nos
LLTCD	Mental State Abnormal Aggravated
PTCD	Mental Status Changes
PTCD	Mini Mental Status Examination Abnormal

MedDRA level	MedDRA Term Label
PTCD	Presenile Dementia
PTCD	Retrograde Amnesia
PTCD	Senile Dementia
LLTCD	Senile Dementia Nos
LLTCD	Short-term Memory Loss
PTCD	Thinking Abnormal
LLTCD	Thinking Slowed
PTCD	Transient Global Amnesia
PTCD	Vascular Dementia

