9.3.3. Infusion Reactions

Infusion reactions are defined as any AE that occurs during the infusion or within 2 hours after the infusion is completed. All infusion reactions must be reported as AEs (defined in Section 9.4.1) and graded using the grading scales as instructed in Section 9.5.1.

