9.4.3. Other Events that Require Accelerated Reporting to Sponsor

The following events also require reporting to the sponsor (or designee) within 24 hours of learning of the event:

Symptomatic Overdose of Study Drug: Accidental or intentional overdose of at least 2 times the intended dose of study drug within the intended therapeutic window, if associated with an AE.

Pregnancy: Although pregnancy is not considered an AE, it is the responsibility of the investigator to report to the sponsor (or designee), within 24 hours of identification, any pregnancy occurring in a female patient, or female partner of a male patient, during the study or within 24 weeks of the last dose of study drug. Any complication of pregnancy affecting a female study patient, or the female partner of a male study patient, and/or fetus and/or newborn that meets the SAE criteria

must be reported as an SAE. Outcome for all pregnancies should be reported to the sponsor.

Adverse Events of Special Interest: All AESI, serious and nonserious, must be reported within 24 hours of identification using the same reporting process as for SAE reporting, per Section 9.4.2. Adverse events of special interest for this study include the following:

- Anaphylactic reactions
- Allergic reactions and/or local injection site reactions that require consultation with another physician for further evaluation
- Increase in ALT or AST: $\geq 3 \times$ ULN (if baseline $<$ ULN), or ≥ 2 times the baseline value (if baseline \geq ULN)
- Pregnancy
- Symptomatic overdose with evinacumab
- Neurocognitive events
- New onset of diabetes: The definition of new onset of diabetes will be the following:
 - Type 1 or type 2 diabetes TEAE (grouping of Medical Dictionary for Regulatory Activities [MedDRA®] terms will be specified in the SAP)and/or
 - At least 2 values of HbA1c $\geq 6.5\%$ during the TEAE period. **NOTE:** For patients with only a single measurement available during the TEAE period, a single value $\geq 6.5\%$ will be considered and qualify the patient as new onset of diabetes by default. For patients with several HbA1c measurements but only with the last one $\geq 6.5\%$, this single value $\geq 6.5\%$ will be considered and qualify the patient as new onset of diabetes by default.and/or

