4.8.1.2. Adverse Events of Special Interest

Adverse events of special interest (AESI) are AEs (serious or non-serious) required to be monitored, documented, and managed in a pre-specified manner. AESIs will be recorded on the adverse event e-CRF using dedicated tick boxes, and/or identified using standard MedDRA queries (SMQ), and/or company MedDRA queries (CMQ), and/or applicable laboratory assessments. [Appendix 10.2](#) contains the definitions used to identify AESIs:

The AESIs include the following:

- Anaphylactic reactions (CRF)
- General allergic events (SMQ)

- Infusion reactions (CRF)
- Pregnancy (CRF)
- Symptomatic overdose with investigational medicinal product (CRF)
- Neurocognitive events (CMQ)
- New onset of diabetes (NOD) (lab data)
- Pancreatitis (CRF)

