5.8.2. Analysis of Adverse Events of Special Interest

Treatment-emergent adverse events of special interest (AESI), as listed in Section 4.8.1.2, will be presented by SOC and PT, if applicable. AESI are defined by SMQ, CMQ, dedicated e-CRF, or lab data as described in [Appendix 10.2](#).

The following variables will also be tabulated for infusion reactions TEAEs:

- Intensity of the event (mild, moderate, and severe);
- Number of events divided by the number of study treatment administrations received in respective treatment periods;
- Time from first study treatment administration (DBTP or SBTP depending on the analysis) to first infusion reaction;

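### The SAP's AESI list has no row for the protocol's ALT/AST increase or local site reactions, so the protocol-defined AESI counts by arm are not tabulated

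*SAP*

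**What the plan says.** Protocol 9.4.3 requires all AESIs, serious or not, to reach the sponsor within 24 hours. Its list includes "Increase in ALT or AST", defined as at least 3x ULN when baseline is below ULN, or at least twice baseline when baseline is at or above ULN. It also includes "Allergic reactions and/or local injection site reactions that require consultation with another physician for further evaluation".

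SAP 4.8.1.2 opens its own list with "The AESIs include the following" and names eight items: anaphylactic reactions, general allergic events, infusion reactions, pregnancy, symptomatic overdose, neurocognitive events, new-onset diabetes and pancreatitis. The table in SAP 10.2 has the same eight rows. It defines general allergic events by the hypersensitivity SMQ, "excluding the following preferred terms linked to local injection site reactions". Nine terms are removed: four infusion-site terms and five injection-site terms.

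SAP 5.8.2 fixes what is tabulated: "Treatment-emergent adverse events of special interest (AESI), as listed in Section 4.8.1.2, will be presented by SOC and PT, if applicable".

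**The concern.** The protocol and SAP lists both have eight items, so the difference is easy to miss. The ALT/AST item has gone, infusion reactions have come in, and the local-reaction half of the allergic item has been taken out without a row of its own.

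At stake is agreement between two records of the same events. Sites will report ALT/AST rises and consulted site reactions as AESIs under the protocol definition. The SAP's AESI tables will not count them under that definition, so a reader comparing the arms will find no row that matches those reports.

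**Working it through.** The documents give no figure to reproduce. The check compares the definitions and then asks whether another planned output gives the missing counts.

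**1. Lists side by side**

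| Protocol 9.4.3 | SAP 4.8.1.2 and 10.2 |
|---|---|
| ALT/AST increase | no row |
| Allergic reactions needing consultation | SMQ query, no consultation criterion |
| Local site reactions needing consultation | nine terms removed from the query, no row |
| not in the AESI list | infusion reactions (CRF) |

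The remaining items correspond by name. SAP 4.8.1.2 already allows AESIs to be identified from laboratory data, and new-onset diabetes uses that route. The missing ALT/AST row is therefore not forced by a lack of data.

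**2. Do the PCSV bands give the ALT/AST count?**

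Let b be baseline and p the post-baseline value, both in multiples of ULN.

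- Protocol AESI: p ≥ 3 if b < 1; p ≥ 2b if b ≥ 1.
- SAP 10.3 PCSV band t: p > t and b ≤ t, for t = 2, 3, 5, 10, 20.

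Exclusion criterion 19 puts entry values below 3x ULN, so take b < 3:

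- b < 1: p ≥ 3, so the >2 band flags it.
- 1 ≤ b ≤ 2: p ≥ 2b ≥ 2, so the >2 band flags it, except at exactly b = 1, p = 2.
- 2 < b < 3: p ≥ 2b > 4, so the >3 band flags it.

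Together the bands miss only the point 1.0 to 2.0x ULN. A grid in steps of 0.05 (b from 0.2 to below 3, p from 0.2 to 12) agrees: 9,376 AESI cells, 1 missed, and 10,820 cells flagged by at least one band. Of the flagged cells, 1,445 are not AESIs (9,376 − 1 + 1,445 = 10,820). These counts show coverage of the definitions; they are not expected patient frequencies.

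Worked cases:

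| b to p (x ULN) | p/b | Protocol AESI | >2 band | >3 band |
|---|---|---|---|---|
| 1.2 to 2.5 | 2.08 | yes | yes | no |
| 0.8 to 3.0 | 3.75 | yes | yes | no |
| 1.0 to 2.0 | 2.00 | yes | no | no |
| 0.9 to 2.7 | 3.00 | no (p < 3) | yes | no |
| 1.9 to 2.1 | 1.11 | no | yes | no |
| 2.8 to 3.2 | 1.14 | no | no (b > 2) | yes |

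The >2 band includes rises that are not AESIs. The >3 band omits some AESIs and includes some rises that are not. The PCSV rows also treat ALT and AST separately, whereas the protocol AESI is either enzyme. No band, or sum of bands, equals the protocol count.

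**3. Where does a site reaction coded to one of the nine terms go?**

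| Event | Protocol AESI? | SAP output |
|---|---|---|
| During infusion or within 2 hours | if consultation needed | can appear as an infusion reaction; also TEAE tables |
| Later than 2 hours, consultation needed | yes | no AESI row unless it meets another item; TEAE tables |
| Later than 2 hours, no consultation | no | TEAE tables |

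The 2-hour limit comes from protocol 9.3.3, which defines an infusion reaction as "any AE that occurs during the infusion or within 2 hours after the infusion is completed". The gap is the second row.

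**4. Declaration.** SAP 1.2.4 lists six modifications from the protocol. None concerns AESIs.

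**The case against.** The strongest case against the point is that nothing goes unseen. A reader might infer from the missing rows that liver or site-reaction signals would be lost. The documents do not support that:

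- ALT and AST rises appear in the PCSV summaries, which use unscheduled values too. SAP 5.8.1 adds a hepatic-disorder SMQ table, and SAP 5.8.5 adds an eDISH plot and a Hy's law listing for ALT with bilirubin.
- Every TEAE is tabulated by SOC and PT, so each of the nine terms that occurs has its own line by arm.
- Expedited reporting by sites follows the protocol and does not depend on the SAP.

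All of this stands, and it limits the point to the defined count.

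Two other inferences also fail. Liver is not among the important potential risks in protocol 3.2.1, which names systemic hypersensitivity, immunogenicity and embryofetal toxicity. Nor is every delayed event coded to one of the nine terms a lost AESI, because the protocol requires another physician's consultation.

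It can be argued that the protocol wording says injection site while the drug is given IV. This carries little weight: SAP 10.2 itself groups infusion-site terms under local injection site reactions. It can also be argued that SAP 1.2.4 covers only the protocol's statistical section, and that protocol 10.4.5.1 promises no AESI table. Yet the first two entries in SAP 1.2.4 concern protocol 2.3, so the table is not confined to Section 10, and SAP 5.8.2 does promise AESI tables.

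The argument for keeping local terms out of the hypersensitivity query is sound. The named allergic risk is systemic, and putting the terms back would blur that table.

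**Conclusion.** The point holds as a protocol-to-SAP mismatch in safety tabulation. Two protocol-defined AESIs have no matching SAP row, and the change is undeclared. The ALT/AST loss is one of definition, since the PCSV bands together catch all but the exact 1.0 to 2.0x ULN case and over-include others. The site-reaction loss is narrower still: delayed reactions that needed a consultation and meet no other AESI item.

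The consequence is that AESI counts by arm cannot be read from any planned table in the protocol's own terms, and the AESI tables will not reconcile with the 24-hour reports. The ALT/AST count could be rebuilt by hand from laboratory listings. Safety output is descriptive and the primary analysis is unaffected.

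This assumes that the SAP 4.8.1.2 list is complete, as SAP 5.8.2 and the matching table in SAP 10.2 indicate, and that baseline is below 3x ULN as at entry. The documents do not show whether the CRF records the consultation criterion.

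**What to change.** - **ALT/AST.** Add an "Increase in ALT or AST" row to SAP 4.8.1.2 and 10.2, derived from laboratory data with the two-part definition in protocol 9.4.3 and the pre-double-blind baseline already set in SAP 4.8 and 6.1.
- **Site reactions.** Add a separate row for local infusion or injection site reactions, using the nine excluded terms. Limit it to events needing another physician's consultation if the CRF records this. Otherwise, label the row as broader than the protocol AESI.
- **Allergic events.** Leave the systemic hypersensitivity query unchanged.
- **Declaration.** List any remaining difference from protocol 9.4.3 in SAP 1.2.4.

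The cost is a few lines of SAP text and two extra table rows. The ALT/AST row uses data already collected. The term-based site-reaction row uses coded adverse events, and only its consultation limit depends on the CRF.

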 - At least 2 values of fasting glucose ≥ 126 mg/dL (7.0 mmol/L). **NOTE:** For patients with only a single measurement available during the TEAE period, a single value ≥ 126 mg/dL (7.0 mmol/L) will NOT be considered and will NOT qualify the patient as new onset of diabetes. For patients with several fasting glucose measurements but only with the last one ≥ 126 mg/dL (7.0 mmol/L), this single value ≥ 126 mg/dL (7.0 mmol/L) will NOT be considered and will NOT qualify the patient as new onset of diabetes- Pancreatitis

Refer to the study manual for the procedures to be followed.

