1.2.4. Modifications from the Statistical Section in the Final Protocol

The summary of modifications is listed in the following table.

Item	Protocol Section	Description
1	2.3 Exploratory Objective To assess medical visits/hospitalizations for abdominal pain or pancreatitis, medical visits/hospitalizations for pancreatitis, and medical visits/hospitalizations for cardiovascular disease	SAP Section 1.2.3: Modified exploratory objective for medical visits/hospitalizations to remove medical visits because it is not captured in e-CRF (consistent across all evinacumab studies).
2	2.3 Exploratory Objective	SAP Section 1.2.3, added two objectives: 
• To evaluate changes in the number and percentage of stomach pain, pain and abdominal symptom-free days, defined as the number and percentage of stomach pain free days, number of pain free days, and the number of abdominal symptom free days, as assessed by the HAP-SS.• To evaluate changes in the number and percentage of days where meals are avoided as assessed by the HAP-DB.
3	10.3.2 Safety Analysis Set The safety analysis set (SAF) includes all randomized patients who received any randomized study drug; it is based on the treatment received (as treated). Treatment compliance/administration and all clinical safety variables will be analyzed using the SAF.	SAP Section 3.2 and 3.3: Safety Analysis Set was divided to double-blind and single-blind period to be consistent with other evinacumab studies.
4	10.4.3.1 Primary Efficacy Analysis 
• “For the assessment of probability (computed from the likelihood function based on the observed data, which is equivalent to Bayesian posterior probability with uninformative prior) that mean TG percent change $\geq 40\%$...”• “A natural log transformation will be applied to the TG levels prior to	SAP Section 5.7.1: 
• For this proof-of-concept trial, estimates in TG change will be reviewed for 40% reduction supporting future drug development planning i.e., body of evidence review. Due to a lack of historical data in this indication, the application of posterior probability is not informative.• To provide further clarification, TG baseline definition was changed to the

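### The SAP's new-onset-diabetes count has no baseline condition, so stable pre-existing diabetes can qualify, and it drops the protocol's diabetes-TEAE criterion without recording the change

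*SAP*

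**What the plan says.** SAP 5.8.2 hands the definition of every adverse event of special interest to Appendix 10.2: "AESI are defined by SMQ, CMQ, dedicated e-CRF, or lab data as described in" that appendix. SAP 4.8.1.2 gives the data source for this one as laboratory data ("New onset of diabetes (NOD) (lab data"). SAP 10.2 then sets two criteria joined by OR:

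- At least two HbA1c values of 6.5% or more in the TEAE period. If the patient has only one value, or only the last of several reaches the threshold, that value "will be considered and qualify the patient as NOD by default".
- At least two fasting glucose values of 126 mg/dL (7.0 mmol/L) or more. A single or last value does not suffice.

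Protocol 9.4.3 has the same two laboratory criteria. Its HbA1c note says the value "will be considered and qualify the patient as new onset of diabetes by default"; its glucose note says a lone value "will NOT qualify the patient as new onset of diabetes". It also has a third criterion, joined by and/or: "Type 1 or type 2 diabetes TEAE", for which the grouping of MedDRA "terms will be specified in the SAP".

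SAP 1.2.4 opens its table of departures from the protocol with "The summary of modifications is listed in the following table". The table has six items, and none concerns new-onset diabetes.

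**The concern.** A count of new cases needs a population at risk, meaning patients who did not already have the condition. Neither document supplies one here. The phrase limiting HbA1c values to the TEAE period sets a time window; it does not exclude anyone on baseline status.

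If patients with diabetes enrol, the row can mix existing with new disease and can no longer be read as new cases. The single-blind all-patients column is the most exposed, because it has no concurrent control. In the other direction, a patient reported with diabetes as an adverse event who meets neither laboratory rule counts under the protocol but not under the SAP. The row can therefore be wrong by inclusion and by omission, for an event the sponsor chose to monitor specially.

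**Working it through.** No figure for new-onset diabetes is stated in the plan, so there is none to reproduce. The check is a comparison of texts plus simple arithmetic.

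**1. Can patients with diabetes enter?** Yes. Exclusion 15 (Protocol 6.2.2) names only uncontrolled diabetes, as an example of a condition left to the investigator's judgement. Schedule footnote 11 (Protocol 8.1.1, repeated in SAP 10.4.1) covers morning diabetes medication. SAP 4.2 collects type 1 and type 2 diabetes history, and SAP 4.1 has a baseline HbA1c category of 6.5% or more.

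**2. Does any rule remove them from the count?** SAP 5.8.2 adds no at-risk denominator and SAP 10.2 no baseline condition. Elsewhere the SAP writes such conditions out: the ALT, AST, alkaline phosphatase, total bilirubin and CPK criteria in SAP 10.3 each include one.

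**3. Trace a patient.** Assume, for illustration, a steady HbA1c of 7.0% before and throughout the study.
- *Single-blind period.* The TEAE window runs from the first single-blind dose to the last dose plus 168 days (SAP 4.8.1). With the last dose at day 141, 141 + 168 = day 309, the planned end of study. The week 24 and week 44 HbA1c samples fall inside it. The patient qualifies with no change from baseline.
- *Double-blind period.* For a patient who continues, the window closes the day before the first single-blind dose. The scheduled week 12 HbA1c is taken at that dosing visit, so it falls after the window. On scheduled samples the double-blind count therefore rests mainly on the glucose rule, with chemistry at weeks 2, 4, 6 and 8 in the SAP 10.4 schedule. HbA1c can still contribute through unscheduled values (SAP 6.4) or in patients who do not continue, whose window runs to 168 days after the last double-blind dose.

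**4. Effect of one such patient on the reported rate.** Inputs: up to about 50 patients, randomised 2:1 (SAP 2.1).
- Evinacumab: 50 × 2/3 = 33.3, so 1/33 = 3.0 points.
- Placebo: 50 × 1/3 = 16.7, so 1/17 = 5.9 points.
- Single-blind total if all 50 continue: 1/50 = 2.0 points.

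**5. Do other tables give the right count?**

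| Source | Threshold | Values needed | Baseline split |
|---|---|---|---|
| NOD, SAP 10.2 | HbA1c ≥6.5% | 2, or 1 if only or last | none |
| NOD, SAP 10.2 | fasting glucose ≥126 mg/dL (7.0 mmol/L) | 2 | none |
| Glucose PCSV, SAP 5.8.5 and 10.3 | ≥7 mmol/L fasted | 1 | yes |
| HbA1c PCSV, SAP 5.7.3 and 10.3 | >8% | 1 | none stated |

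The glucose PCSV split comes closest, but it needs only one value and places a patient with treated diabetes and a baseline glucose below the threshold in the normal group.

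**6. The omitted criterion.** The only MedDRA term list in SAP 10.2 is the neurocognitive one. The table in SAP 1.2.4 is not confined to the protocol's Section 10: items 1 and 2 record changes to Protocol 2.3. A change to the criteria in 9.4.3 would have belonged there too.

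**The case against.** The best counter-argument is that the exclusion is already implied. SAP 5.8.2 tabulates treatment-emergent events, SAP 4.8.1.1 limits these to events that arose, worsened or became serious in the period, and the row is labelled as new onset. Stable diabetes fits none of these. The intent is probably as the argument says, but the algorithm is explicit, uses laboratory values and qualifies patients by default. A programmer will code what is written, and general wording elsewhere does not override it.

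Second, patient listings contain all measurements, and HbA1c is summarised by visit and group, so a reader could check each case by hand. That is true and useful, but it does not correct the tabulated count.

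Third, the omitted TEAE criterion is narrow: it matters only for patients with a diabetes adverse event who meet neither laboratory rule, and those events remain in the SOC/PT tables. This stands, and it limits that part of the point to the NOD row.

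Three stronger readings are tempting and unsupported. A reader might infer that the row *is* inflated in both arms. The documents give neither the share of patients with diabetes nor their glycaemic values, so the number affected could be zero in either arm. A reader might infer bias for or against evinacumab; allocation is randomised and nothing in the documents points either way. A reader might also scale the single-blind figure by the plan's 20% drop-out, but Protocol 10.2 and SAP 2.2 use that figure only to go from 24 to 30 patients for the triglyceride analysis.

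**Conclusion.** The point holds as a fault in a stated rule. As written, SAP 10.2 can count stable pre-existing diabetes as new onset, and it loses cases identified only as an adverse event. The gap in baseline conditions comes from the protocol, so adherence to the protocol does not cure it; the loss of the TEAE criterion arises in the SAP and is unrecorded.

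The per-patient effects above assume that the full 50 are enrolled and split 2:1, and that all continue for the single-blind figure. They show how sensitive the row is; they do not estimate the error.

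The consequence is limited. Safety summaries are descriptive, no formal test or stopping rule in the documents depends on this row, and the primary endpoint is untouched. The change should still be made, because this is a designated event of special interest, the arms are small, and the data needed are already collected.

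**What to change.** In SAP 10.2:

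- Restrict both numerator and denominator to patients without diabetes at baseline: no diabetes in the medical history, no glucose-lowering drug taken for diabetes, baseline HbA1c below 6.5% and baseline fasting glucose below 126 mg/dL. Both laboratory limits are needed; with HbA1c alone, a patient already at or above the glucose threshold could still qualify through the glucose rule.
- State the TEAE window in the lead sentence of the glucose criterion, which lacks it in both documents.
- Summarise on-study HbA1c and glucose separately for patients with diabetes at baseline.
- Restore the type 1/type 2 diabetes TEAE criterion with its MedDRA term list, or justify its removal.

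Record these changes in SAP 1.2.4. Align the definition in Protocol 9.4.3 at the next amendment; Protocol 15 requires IRB/EC approval for a protocol change, so this need not prompt an amendment of its own.

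The cost is a smaller denominator for this row, which makes its percentages coarser, and minor programming.
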